11.3 Study Stopping Rules

To reduce the risk of exposing subjects to an excessively toxic dose level, a stopping rule will be implemented if more than 34% of subjects in a given lenalidomide dose cohort experience a DLT. The study ends when there is a dose where 2 or more subjects out of 6 have a DLT, or when the maximum sample size of twenty-four (24) subjects has been reached.

12. DATA AND SAFETY MONITORING

12.1 Summary

This protocol will be reviewed and monitored by the University of Florida Health Cancer Center (UFHCC) Data Integrity and Safety Committee (DISC). This study will have at minimum semi-annual monitoring by the UFHCC DISC. Any adverse event fulfilling

expedited reporting requirements must be reported to the DISC coordinator within 5 working days. The DISC coordinator will forward the report to the DISC Chairperson. If there are any safety concerns, the chairperson will take appropriate action. This may involve a request for additional information, or a request for an early, unscheduled meeting of the DISC.

As part of the responsibilities assumed by conducting this study, the Principal Investigator (PI) agrees to maintain and have available for monitoring adequate case records (accurate source documents and CRFs) for the subjects treated under this protocol.

The PI will be primarily responsible for monitoring of adverse events, protocol violations, and other immediate protocol issues. The study coordinator will collect information on subjects enrolled through the use of electronic or paper adverse event (AE) forms, CRFs, and Informed Consent forms.

Identification of oversight responsibility:

The PI has primary responsibility.

The UFHCC DISC will meet at least semi-annually to review accrual, patterns and frequencies of all adverse events, protocol violations, and when applicable, internal audit results.

Description of internal (PI) safety review and monitoring process:

The PI and study team will meet biweekly to identify and review subject accrual, adverse events, and protocol violations.

Adverse events will be reported along with all of the other collected data in the OnCore database. The PI or PI designee will report all adverse events to the UFHCC DISC and IRB per reporting guidelines.

13. STATISTICAL METHODS

The sections below provide an overview of the proposed statistical considerations and analyses.

13.1 Determinations of Sample Size

No formal sample size calculations were performed. It is estimated that up to 24 subjects will be enrolled in this study. Precise sample size cannot be defined, as it is dependent on the observed toxicity rate. A description of the statistical characteristics (probabilities of halting or continuing dose escalation) of the “3 + 3” design is provided in section 16.7 (Appendix G: Statistical Characteristics of the “3+3” Design). Cohorts of 3 to 6 subjects will be treated at each lenalidomide dose level until the MTD is reached or a total of 24 subjects have been evaluated.

13.2 Analysis Populations

13.2.1 Safety Population

The safety population will consist of all subjects who received at least one dose of study drug and had at least one post-dose safety assessment. Safety summaries will include all subjects in the safety population.

13.2.2 Dose Limiting Toxicity Evaluable Population

A subject is evaluable in dose-escalation decisions provided the subject has received at least five doses without a DLT, has experienced a DLT, or has been withdrawn from the study prior to completing of 21 days of lenalidomide due to a DLT. If a subject withdraws from the study without meeting these criteria, the subject will be replaced in that cohort. Tabulations of DLTs will only include the DLT-evaluable population.

13.2.3 Efficacy Evaluable Population

The efficacy population will include all subjects who receive at least 21 days of study drug and had at least one post-cycle efficacy assessment.

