
Study Design:
	
This is an open-label, phase I dose escalation study of lenalidomide after allo-HCT in AML and MDS subjects with MRD detected by the CD34+ mixed chimerism analysis. The study is designed to evaluate the safety profile, MTD and biologic activity of lenalidomide after allo-HCT in patients with AML and MDS
 
The dose levels of lenalidomide will be as follows:
 
Dose Level 1: 2.5 mg PO QOD Day 1-21 for 28 day cycle X 2 cycles Dose Level 2: 2.5 mg PO QD Day 1-21 for 28 day cycle X 2 cycles Dose Level 3: 5 mg PO QD Day 1-21 for 28 day cycle X 2 cycles Dose Level 4: 7.5 mg PO QD Day 1-21 for 28 day cycle X 2 cycles
 
Subjects will be enrolled in cohorts of three (3). Lenalidomide will be administered for 21 consecutive days in a 28 day cycle X 2 cycles. The starting dose will be 2.5 mg given orally every other day for 21 days.

Subjects will be individually assessed for safety and dose limiting toxicity (DLT) for the purpose of determining the MTD .Three eligible subjects will be enrolled in sequential cohorts at increasing dose levels until at least one DLT is seen between the first dose and 14 days after the last dose of lenalidomide. For this study, MTD will be defined as the highest dose which no more than 34% of the subjects observed at a given dose level experience a DLT. The following dose escalation rules will be used and applied:

1. Three subjects are initially studied at each dose level.
2. If none of these 3 subjects experience DLT, then the dose is escalated to the next dose level in 3 subsequent subjects.
3. If 1 of these 3 subjects experiences DLT at current dose, then up to 3 more subjects are accrued at the same level.
 - a) If none of these 3 additional subjects experience DLT, then the dose is escalated to the next dose level in 3 subsequent subjects.
 - b) If 1 or more of these 3 additional subjects experiences DLT, then the MTD is considered to have been exceeded and the previous dose level will be the MTD.
4. If 2 or more of the initial 3 subjects at a dose level experience DLT, then the MTD is considered to have been exceeded and dose escalation will be stopped. Up to 3 more subjects are treated at the next lower dose.

A subject must meet one of the following 3 criteria to be evaluable for subsequent dose-escalation decisions:

1. Complete at least 21 days of lenalidomide without a DLT by 14 days after the last dose of lenalidomide;

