Statistical Procedures:	This study is descriptive in nature and not designed to provide analytical inferential results regarding primary or secondary endpoints. The sample size is based primarily on clinical considerations and not on statistical power calculations. Statistical characteristics of the “3 + 3” design are described in Appendix G. Descriptive statistics will be used to summarize baseline subject characteristics, treatment administration, and safety variables. All subjects who receive at least 5 doses of lenalidomide and have one post-dose safety assessment will comprise the safety population. The efficacy evaluable population will comprise all subjects who complete

	at least 15 days of lenalidomide and have at least one post-therapy CD34+ specific chimerism assessment.
--	--

Schedule of Events

Assessment	Screening (+/-7 days from Day +60)	Post- Transplant Monitoring Days +60 & 90 (\pm 7 days)	Revlimid C1D1, C2D1	End of Treatment 30 Days post- last Revlimid Dose (\pm 2 days)	Post- Revlimid Monitoring Days +60 & +120 (\pm 7 days)	Survival Every 3-months for 1 year
Signed Informed Consent	X					
Demographics, Medical /Treatment History	X					
MDS and AML WHO Classification	X					
Weight, Height	X					
Physical Examination	X	X	X	X	X	
GVHD Assessment ^A	X	X	X	X	X	
Vital Signs	X	X	X	X	X	
Karnofsky Performance Score	X	X	X	X	X	
CBC + Differential	X	X	X	X	X	
Serum Chemistry	X	X	X	X	X	
Serum Pregnancy Test (females) ^B	X		X			
Bone Marrow Aspiration and Biopsy ^C	X					
Peripheral Blood Chimerism		X				
Peripheral blood CD34+ donor chimerism ^D		X			X	
Dispense Revlimid (21-day supply)			X			
Concomitant Medications	X	X	X	X		
Adverse Events Assessments	X	X	X	X		
Concomitant Blood Products	X	X	X	X		
Disease Response Assessment ^C	X	X				X
Survival Assessment				X		X

- A. Overall grading and response to GVHD therapy will be measured through the use of the consensus and IBMTR GVHD severity indices. GVHD assessments will be performed at screening and Days +60 & +90. If lenalidomide is initiated, GVHD assessments will be performed weekly during scheduled visits and continuing until 30 days after the last dose of lenalidomide. GVHD assessments will also be documented at Days +60, and Day +120 after the initiation of lenalidomide.

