9.1.2 Correlative Studies

The CD34+ specific chimerism analysis from peripheral blood will be performed on days +60 and +90 (± 7 days) post-HCT until the CD34+ donor chimerism drops to $\leq 90\%$ and/or on days +60 and +120 (± 7 days) days after the initiation of lenalidomide. Additional CD34+ donor chimerism testing will be performed at the discretion of the clinical investigator (*e.g.*, when a subject develops peripheral blasts, worsening pancytopenia, or extramedullary relapse).

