11. DISCONTINUATIONS

11.1 Discontinuation of Subjects

A subject must be discontinued from protocol-prescribed therapy under the following circumstances:

- Consent withdrawal at the subject's own request or at the request of their legally authorized representative;
- Unacceptable toxicity or adverse event as determined by the Principal Investigator and/or subject;
- Significant deviation from inclusion/exclusion criteria, in the opinion of the Principal Investigator;
- If, in the Principal Investigator's opinion, continuation in the study could be detrimental to the subject's well-being;
- Relapsed or progressive disease;
- Initiation of chemotherapy for relapsed or progressive disease.

If a female subject or the female partner of a male subject who is required to use defined contraceptive methods becomes pregnant after the study, the female subject or pregnant partner must be followed until the outcome of the pregnancy is known.

As far as possible, all end-of-study examinations must be performed on all subjects who receive the study drug but do not complete the study according to protocol. All subjects who discontinue from protocol-prescribed therapy for any of the reasons above will be followed for a period of 30 days following the last day of study drug administration.

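### The efficacy-evaluable population has two conflicting definitions, neither is named as the denominator of the chimerism reversal rate, and no rate in all dosed subjects stands beside it

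*Combined protocol and SAP*

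**What the plan says.** **Population.** The Synopsis (Statistical Procedures) admits subjects with "at least 15 days of lenalidomide and have at least one post-therapy CD34+ specific chimerism assessment". Section 13.2.3 says: "The efficacy population will include all subjects who receive at least 21 days of study drug and had at least one post-cycle efficacy assessment". Neither text refers to the other.

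**Outcome and analysis.** The Synopsis (Efficacy Assessments) names one efficacy outcome, reversal of the fall in CD34+ donor chimerism by day 60 of lenalidomide. Section 13.3.2 plans frequency distributions and 95% confidence intervals for proportions, and names no analysis population. The safety population of Section 13.2.1 starts from a single dose, but it is assigned to safety summaries.

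**Early stopping.** Section 11.1 ends protocol therapy for relapse or progression and for unacceptable toxicity, among other reasons. Section 11.2 replaces anyone withdrawn before completing 21 days.

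**Testing after a stop.** Section 9.1.2 sets the tests at +60 and +120 (±7) "days after the initiation of lenalidomide". Footnote D of the Schedule of Events asks for them in subjects receiving lenalidomide, and Section 8.1 applies the Schedule to all subjects. Section 11.1 says that subjects who discontinue "will be followed for a period of 30 days following the last day of study drug administration".

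**The concern.** A subject with 15 to 20 days of drug and a chimerism result is in the Synopsis set and outside the Section 13.2.3 set. With no governing text, the choice between them can be made after the results are known.

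Separately, both definitions select on what happens after the first dose. Someone who relapses, progresses or stops for toxicity before the minimum exposure leaves the denominator and is replaced by a new subject. If those lost are non-reversals, the reported proportion is too favourable. For toxicity stops the direction is uncertain. No planned output shows how many dosed subjects were left out or what the rate would be with them in.

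The reversal proportion is the only efficacy rate that the plan names, and the Synopsis rationale presents the study as the foundation for a phase II trial, so the figure is likely to be reused.

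**Working it through.** **1. The plan's own figures.** None exist for this endpoint: no assumed reversal rate, dropout rate or power. The only computed figures are the 3+3 probabilities in Appendix G. They reproduce from (1−p)³ + 3p(1−p)²·(1−p)³ (at p = 0.2: 0.7086, stated 0.71), and nothing here depends on them.

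**2. The definitions side by side.**

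| | Synopsis | Section 13.2.3 |
|---|---|---|
| Exposure | at least 15 days | at least 21 days |
| Assessment | CD34+ chimerism, post-therapy | efficacy assessment, post-cycle, not named |

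On exposure the sets are nested. The unnamed assessment is probably chimerism, but the Schedule also lists a disease response assessment.

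**3. What is a day of drug?** The Synopsis says "The starting dose will be 2.5 mg given orally every other day for 21 days". At that level a cycle holds 11 doses (days 1, 3, …, 21), so two cycles hold 22. Counted as calendar days, 21 days is one cycle. Counted as dosing days, it is 21 of 22 doses, reached on study day 47 (the 10th dose of cycle 2, 28 + 19) if none is missed. Section 6.1 gives a total of 42 days, which fits calendar days (2 × 21), but neither population definition says so.

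**4. Effect of conditioning on exposure (all counts assumed).** Take the maximum of 24 dosed (Section 5.1) with 6 reversals: 6/24 = 25.0%, exact 95% CI 9.8 to 46.7%, width 36.9 points. Exclude k subjects, of whom r reversed. The evaluable rate is (6 − r)/(24 − k).

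| k | r = 0 | r = k/2 |
|---|---|---|
| 2 | 6/22 = 27.3% (+2.3) | 5/22 = 22.7% (−2.3) |
| 4 | 6/20 = 30.0% (+5.0) | 4/20 = 20.0% (−5.0) |
| 6 | 6/18 = 33.3% (+8.3) | 3/18 = 16.7% (−8.3) |

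With the all-dosed rate held fixed the two columns mirror each other. If those excluded reversed at 25%, nothing moves (k = 4, r = 1: 5/20 = 25.0%).

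**5. Effect of 15 versus 21 days (all counts assumed).** Start from 6/20 = 30.0% (11.9 to 54.3%) in the 21-day set and add m subjects with 15 to 20 days and a chimerism result.

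| m | none reversed | all reversed |
|---|---|---|
| 1 | 6/21 = 28.6% (−1.4) | 7/21 = 33.3% (+3.3) |
| 2 | 6/22 = 27.3% (−2.7) | 8/22 = 36.4% (+6.4) |
| 3 | 6/23 = 26.1% (−3.9) | 9/23 = 39.1% (+9.1) |

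If they reverse at the same 30%, the expected rate is (6 + 0.3m)/(20 + m) = 30%, so the shift is zero on average. If nobody falls in the 15-to-20-day band, the two exposure limits give the same set.

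**6. Would early stoppers have a day +60 result?** The window is days 53 to 67 (60 ± 7). In calendar days, a last dose on days 15 to 20 puts the end of 30-day follow-up at days 45 to 50. Day 21 gives day 51, or day 53 using the +2 days of the End of Treatment visit. A last dose on day 29 gives day 59, inside the window. Section 11.1 asks that, as far as possible, "all end-of-study examinations must be performed on all subjects who receive the study drug but do not complete the study", but the Schedule row "Peripheral blood CD34+ donor chimerism" has no mark at End of Treatment. Section 9.1.2 adds: "Additional CD34+ donor chimerism testing will be performed at the discretion of the clinical investigator". Against this, Section 9.1.2, Section 8.1 and footnote D make no exception for early stops. The passages leave the matter open, mainly for stops in cycle 1.

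**The case against.** The strongest reply is that little hangs on this. The Synopsis disclaims inferential aims, the secondary objective is to monitor changes in chimerism, which needs a measurement after baseline, and nothing promises an all-dosed rate. That limits the weight of the point. It does not settle which of two definitions applies to an interval that the plan says it will report.

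A reader might infer from step 6 that early stoppers lose their day +60 test. The documents do not support that. Three places call for the test in treated subjects without exception, and one states a 30-day follow-up. This is something to reconcile, not a demonstrated loss of data.

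A reader might also add the two harms together. In calendar days they largely need opposite readings. The 15-versus-21 choice matters only if subjects in that band have a chimerism result; if follow-up ends before the test and no discretionary test is done, they fall outside both sets.

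Nor do the documents show that the evaluable rate is inflated. Step 4 gives equal shifts either way, and the extreme of +9.1 points in step 5 needs three short-exposure subjects who all reversed.

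It is also true that the Synopsis gives no numeric threshold for reversal, so settling the denominator does not by itself settle the proportion.

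**Conclusion.** The conflict is plain in the current text, and confidence in it is high. As written, the reversal proportion and its interval cannot be produced without a choice that the plan leaves open. That the evaluable rate can be biased by conditioning on exposure follows from the definitions and Sections 11.1 and 11.2; the size and direction in this trial cannot be derived from the documents.

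Under the assumed counts, selection moves the rate by 2.3 to 8.3 points in either direction and the choice of exposure limit by −3.9 to +9.1 points. Both are small against an interval about 37 points wide at 6/24. The endpoint is secondary and descriptive, and MTD decisions do not use this population. The correction should be made, but it does not threaten the primary objective.

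**What to change.** Before data review:

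- State one exposure criterion and one named assessment (a CD34+ chimerism result) in identical words in the Synopsis and Section 13.2.3. Define a day of exposure so that it also works for every-other-day dosing.
- In Section 13.3.2, name that set as the denominator.
- Add one row with the reversal proportion and exact 95% CI in all subjects who received at least one dose. Count relapse, death or new anti-leukemia therapy before the day +60 assessment as not reversed. Give the number without a result for other reasons, with the lowest and highest possible rate: for example, 6 reversed, 14 not and 4 unknown gives 6/24 = 25.0% to 10/24 = 41.7%. Write out at least one dose rather than citing the safety population, because the Synopsis sets that at five doses and Section 13.2.1 at one.
- Reconcile Section 8.1, Section 9.1.2 and footnote D with Section 11.1 on testing after early discontinuation. This review does not say which should prevail and asks for no extra visits.

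The cost is wording in a few sections, one counting rule and one table row. The all-dosed row needs no new data. The drawback is a conservative and possibly less favourable rate if some subjects without a result had in fact reversed.

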13.3 Analysis Methods

13.3.1 Safety

Safety evaluation will include monitoring for adverse events, scheduled laboratory assessments, vital sign measurements, and physical examinations. The intensity of adverse changes in physical signs or symptoms will be graded according to the CTCAE version 4. For all other adverse events not listed in the CTCAE, the intensity of these events will be assessed by the Investigator using a 5-point scale as described in Section 10.3.2.

The number of adverse events and the incidence of adverse events will be summarized. Adverse events will be summarized by maximum intensity (as described in Section 10.3.2) and relationship to study drug for each treatment group. Separate summaries will be provided for all adverse events, serious adverse events, treatment-related adverse events, and other significant adverse events (*e.g.*, adverse events leading to study discontinuation).

Clinical laboratory results will be listed by subject or, as appropriate, summarized descriptively by treatment group, which will include a display of change from baseline. Laboratory values outside of the normal ranges will be identified. Clinically significant hematologic laboratory abnormalities (*i.e.*, meet Grade 3, 4, or 5 criteria according to CTCAE v.4) will be listed and summarized.

Physical examination, vital sign, and GVHD data will be listed for each subject at each study visit. If appropriate, descriptive statistics for vital signs, both observed values and changes from baseline, will be summarized by treatment group.

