4.3 Dose Limiting Toxicity

DLT will be defined as any of the following adverse events that are not clearly unrelated to drug administration or treatment-emergent from lenalidomide and constitute a change from baseline irrespective of outcome. For the purpose of dose-escalation decisions and MTD determination, only DLTs that occur before 14 days after the last dose of lenalidomide administration will be taken into account.

1. Grade 3 or greater nausea, diarrhea, or vomiting despite the use of maximal medical intervention;
2. Grade 3 or greater acute GVHD despite the use of maximal medical intervention;
3. Any other clinically significant nonhematologic toxicity of grade 3 or greater considered not related to the underlying disease or intercurrent illness;
4. Grade 3 or greater neutropenia
5. Grade 4 thrombocytopenia or platelet count ≤ 50 thou/mm³ by day 28 of lenalidomide administration; or
6. Any treatment-related effect leading to a subject missing 3 or more doses of lenalidomide.

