9.2.2.2 Clinical Laboratory Measurements

All clinical laboratory assessments are outlined in the Schedule of Events.

Hematology assessments will be performed at Screening and then weekly during lenalidomide administration and for 3 weeks after therapy is completed. The hematology assessments will include:

- Complete blood count including hemoglobin, hematocrit, WBC absolute differential and platelet count.

Blood chemistry assessments will be performed at screening and then weekly during lenalidomide administration. The chemistry assessments will include:

- Electrolytes: (sodium, potassium, calcium, magnesium, phosphorous, bicarbonate, and chloride);
- Renal function: (BUN, creatinine, and uric acid);
- Liver function: SGOT (also known as AST), SGPT (also known as ALT), total bilirubin; and
- Alkaline phosphatase.

Serum pregnancy test for females of childbearing potential will be performed at Screening and must follow the pregnancy testing requirements as outlined in the Revlimid REMS® program material.

Abnormal values and/or noteworthy changes will be graded according to the Common Terminology Criteria for Adverse Events v4.0 (CTCAE).

Abnormalities of laboratory values:

The Investigator shall classify laboratory values occurring outside of the normal range obtained for the safety assessment as:

- “Abnormal, but not clinically significant” or
- “Abnormal and clinically significant”

Laboratory abnormalities should be judged as “clinically significant” if they lead to treatment modifications, therapeutic actions, or if additional diagnostic measures are required for their resolution and in the Investigator’s opinion is relevant for the clinical study.

Each clinically relevant laboratory abnormality must be recorded as a separate AE if it fits within the AE criteria outlined in Section 10.1 of the protocol and is not already described by another documented AE.

Hematology and serum chemistry assessments will be performed according to the standard operating procedures by the validated local laboratory.

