10.1.5 Abnormal Laboratory Values

The investigator must appraise all abnormal laboratory results for their clinical significance. If any abnormal laboratory result is considered clinically significant, the investigator must provide details about the action taken with respect to the test drug and about the patient's outcome.

An abnormal laboratory value is considered to be an AE if the abnormality:

- Results in discontinuation from the study;
- Requires treatment, modification/ interruption of IP dose, or any other therapeutic intervention;
- Or is judged to be of significant clinical importance.

Regardless of severity grade, only laboratory abnormalities that fulfill a seriousness criterion need to be documented as a SAE. If a laboratory abnormality is one component of a diagnosis or syndrome, then only the diagnosis or syndrome should be recorded on the AE CRF. If the abnormality was not a part of a diagnosis or syndrome, then the laboratory abnormality should be recorded as the AE. If possible, the laboratory abnormality should be recorded as a medical term and not simply as an abnormal laboratory result (*e.g.*, record thrombocytopenia rather than decreased platelets).

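### Section 13.3.1 plans a Grade 3–5 laboratory summary for hematology only; a Grade 3+ chemistry value reaches a graded summary only if it is recorded as an AE or DLT

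*Combined protocol and SAP*

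**What the plan says.** **Section 13.3.1 (Safety).** The grade-based laboratory output covers "Clinically significant hematologic laboratory abnormalities", which the same sentence equates with values that "meet Grade 3, 4, or 5 criteria according to CTCAE v.4) will be listed and summarized". All other laboratory results go either into a per-subject listing or, where suitable, into a descriptive summary by treatment group with change from baseline. Out-of-range values are flagged. AEs are tabulated by maximum intensity and by relationship to drug.

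**Section 9.2.2.2 (Clinical Laboratory Measurements).** "Blood chemistry assessments will be performed at screening and then weekly during lenalidomide administration". The panel covers electrolytes, renal function, liver function (AST, ALT, total bilirubin) and alkaline phosphatase. Grading is not confined to blood counts: "Abnormal values and/or noteworthy changes will be graded according to the Common Terminology Criteria for Adverse Events v4.0 (CTCAE"). The section also defines clinical significance, by treatment modification, therapeutic action or extra diagnostic work together with the investigator's opinion that the finding is relevant.

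**Section 10.1.5 (Abnormal Laboratory Values).** "An abnormal laboratory value is considered to be an AE if the abnormality" leads to discontinuation from the study, needs treatment or a change or interruption of study drug, or is judged clinically important. If it belongs to a diagnosis or syndrome, only that diagnosis or syndrome is recorded.

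**Section 4.3 (Dose Limiting Toxicity), item 3.** "Any other clinically significant nonhematologic toxicity of grade 3 or greater considered not related to the underlying disease or intercurrent illness".

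**The concern.** The two laboratory domains are collected side by side and graded on the same scale, but only one is reported by grade. For hematology, the Grade 3–5 table depends on the measured value alone. For chemistry, whether a Grade 3+ value is counted in any graded summary depends on whether the investigator acted on it or thought it important.

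Safety is part of the primary objective (Section 3.1), and the safety summaries by dose level are the main product of a descriptive phase I study. If some Grade 3+ hepatic, renal or electrolyte values are left ungraded, a reader of those summaries cannot tell a dose level with no such values from one where they occurred but were judged unimportant.

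**Working it through.** No formula applies and the plan states no figure to reproduce. The check is to follow a single Grade 3+ laboratory value through every safety output that the plan describes.

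**Outputs available** (Sections 13.2.2 and 13.3.1): the laboratory listing or descriptive summary; the normal-range flag; the Grade 3–5 laboratory listing and summary; the AE tables by maximum intensity; the DLT tabulation.

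| Value | Grade 3–5 laboratory summary | AE table by intensity | DLT tabulation | Ungraded listing or summary, with flag |
|---|---|---|---|---|
| Grade 3+ hematology | Yes, whatever the investigator's view | If recorded as an AE | If it meets 4.3 | Yes |
| Grade 3+ chemistry, recorded as an AE | No | Yes | If it meets 4.3 | Yes |
| Grade 3+ chemistry, part of a diagnosis | No | The diagnosis is graded; the laboratory grade is not shown | If the diagnosis meets 4.3 | Yes |
| Grade 3+ chemistry, no action taken and judged not important | No | No | No | Yes, and nowhere else |

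**Why the last row can occur.** Section 10.1.5 lists three triggers: discontinuation; treatment, dose change or other intervention; judged importance. Section 10.1.1 adds, as an example of a clinically significant finding, one that needs unscheduled diagnostic procedures. None of these is a grade. A Grade 3 value that is watched until it settles, with no intervention or extra work-up, need not become an AE. It cannot then be a DLT either, because Section 4.3 builds DLTs from adverse events and item 3 also requires clinical significance.

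**What remains for that value.** The flag is against the normal range, so a slight excursion and a Grade 3 value carry the same mark. The per-subject listing is one of two alternatives in Section 13.3.1, not a firm commitment. A descriptive summary of change from baseline does not identify a graded event.

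**One term, two meanings.** Section 13.3.1 equates clinical significance with Grade 3–5 for hematology. Section 9.2.2.2 defines it by the action taken and the investigator's opinion. This matters for how the fix is worded.

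**Scale.** Section 13.1 plans 3 to 6 subjects per dose level. One affected subject is 1/6 = 17% to 1/3 = 33% of a level. That is the weight of any single-subject event in so small a cohort, not an estimate of how often the gap would arise.

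**The case against.** The strongest reply is that little falls through. The AE route is wide: treatment, dose modification or interruption, discontinuation, unscheduled diagnostics or judged importance each bring a chemistry value in, and Section 10.1.5 obliges the investigator to appraise every abnormal result. Once recorded, the value is tabulated by maximum intensity. With at most 24 subjects, a per-subject listing with flags would let a careful reader find the rest. Limiting the graded table to hematology also fits the DLT definition: items 4 and 5 in Section 4.3 rest on stated grades or counts, while item 3 requires clinical significance and so runs through AE recording. The study is declared descriptive.

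Most of this stands, and it rules out several stronger readings:

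- A reader might infer that Grade 3+ chemistry values appear in no graded safety table. That is not so, because those recorded as AEs do, and some would also be DLTs.
- A reader might infer that liver GVHD could go unreported. Bilirubin does stage it (Appendix F), but Section 13.3.1 lists GVHD data for each subject at each visit, whatever the laboratory table covers.
- A reader might infer that nothing checks the investigator's judgment under DLT item 3. Section 12.1 provides biweekly review by the study team and at least semi-annual review by the Data Integrity and Safety Committee. An end-of-study table would not alter DLT decisions made during escalation.

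What the reply does not remove is the difference in treatment. The plan gives no reason why a graded hematology value is summarized regardless of judgment while a graded chemistry value is not, and the listing that might compensate is optional and ungraded.

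**Conclusion.** The point holds in a limited form. No laboratory-based Grade 3–5 summary is planned for chemistry. A Grade 3+ chemistry value that is neither acted on nor judged important is left out of every graded summary, and one recorded under a diagnosis loses its own grade. The consequence is incomplete reporting of the safety profile by dose level, not an error in dose escalation.

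Its size cannot be quantified from the documents, which give no rate of Grade 3+ chemistry values or of how often investigators judge such values unimportant. The conclusion assumes that the grading in Section 9.2.2.2 is applied to chemistry as written, wherever CTCAE defines a grade for the test, and that treatment group in Section 13.3.1 means dose level. This is a low-priority improvement, worth making because it is nearly free.

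**What to change.** Replace the sentence in Section 13.3.1 with wording such as: *All hematology and chemistry values of CTCAE v.4 Grade 3, 4 or 5 will be listed and summarized by dose level, with an indication of which were reported as AEs and which as DLTs.*

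Drop both the restriction to hematology and the reference to clinical significance. Deleting only the first would extend to chemistry a definition of clinical significance that conflicts with Section 9.2.2.2.

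The cost is one reworded sentence, some additional table rows and two indicator columns, from data that the trial already collects and grades. No additional sampling is needed, and no sample size, error rate or escalation rule changes.
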